1. ABBREVIATIONS

Abbreviation	Explanation
AE	adverse event
AR	adverse reaction
BDA	British Dietetic Association
CI	chief investigator
CNAQ	Comprehensive Nutrition Assessment Questionnaire
CONSORT	Consolidated Standards of Reporting Trials
CRF	case report form
CRP	C-reactive protein
CTRU	Clinical Trials Research Unit
DMEC	Data Monitoring and Ethics Committee
DSUR	Development Safety Update Report
FBC	full blood count
FC	faecal calprotectin
FODMAP	fermentable olig-, di-, and mono-saccharides and polyols
GCP	Good Clinical Practice
GP	general practitioner
GSRS-IBS	Gastrointestinal Symptom Rating Scale-IBS
HADS	Hospital Anxiety and Depression Scale
IBD-Q	Inflammatory Bowel Disease Questionnaire
IBS	irritable bowel syndrome
ID	identification
IME	important medical event
IMP	investigational medicinal product
MAMS	multi-arm multi-stage
MHRA	Medicines and Healthcare products Regulatory Agency
NHS	National Health Service
NICE	NICE National Institute for Health and Care Excellence
OD	once daily
PI	principal investigator
PIC	Participant Identification Centre
PIS	participant information sheet
RCT	randomised controlled trial
REC	research ethics committee
RGF	Research Governance Framework
RSI	reference safety information
RUSAE SAE	related unexpected serious adverse event serious adverse event
SAP SAR	statistical analysis plan serious adverse reaction
SAR SD	senous adverse reaction standard deviation
	Stanuaru UEVIALIUTI

SOP	standard operating procedure
SPC	summary of product characteristics
SUSAR	suspected unexpected serious adverse reaction
ТСА	tricyclic antidepressants
TMG	Trial Management Group
ToR	terms of reference
TSC	Trial Steering Committee
tTG	tissue transglutaminase
UC	ulcerative colitis

TRIAL SUMMARY

Title	Managament of diarrhage in ulgerative solities multi-arm multi-atage trial of			
Title	Management of diarrhoea in u lcerative colitis: multi-arm multi stage trial of low FODMAP diet, a mitriptyline, ondanse t ron, or lop e ramide			
Short title	MODULATE			
Chief	[name]			
Investigator				
Trial design	Pragmatic, seamless, phase 2/3, open, parallel group, multi-arm multi-stage (MAMS) randomised controlled trial (RCT), with internal pilot.			
Background	In participants with ulcerative colitis (UC), residual problems of diarrhoea and urgency during periods of stable disease can still affect participants. However, the best treatments for these symptoms, which can have both substantial negative physical and emotional impact, is unclear.			
Target sample	A maximum of 491 participants (396 in phase 2 and up to 95 in phase 3)			
size and setting	from approximately 26 secondary care settings.			
Duration	25 months recruitment (including 12-month internal pilot) and 12 months follow-up.			
Patient population	Inclusion criteria: ≥18 years; stable UC with at least moderate discomfort from diarrhoea according to the Gastrointestinal Symptom Rating Scale-IBS (GSRS-IBS) questionnaire (equating to a score of ≥4 on the diarrhoea subscale), C-reactive protein (CRP) <5mg/L, faecal calprotectin (FC) <250mcg/g and endoscopic Mayo score >1 at sigmoidoscopy (if performed due to clinical uncertainty).			
	Exclusion criteria: Previous or planned gastrointestinal surgery; active UC (CRP ≥5mg/L, FC ≥250mcg/g or endoscopic Mayo score >1 at sigmoidoscopy (if performed due to clinical uncertainty or rectal bleeding)); BMI≤18.5kg/m ² ; steroids within the last 2 months; coeliac disease; previous colorectal cancer or dysplasia; allergy/contraindication to, or previous failed trial of, study interventions; pregnancy/breastfeeding.			
	Please refer to section 5 for the full list of inclusion and exclusion criteria.			
Intervention:	Participants will receive one of the following active interventions for 6 months:			
	1. Low fermentable oligo-, di-, and mono-saccharides and polyols (FODMAP) diet for 8 weeks, with FODMAP reintroduction to tolerance for the remaining 4 months for longer term symptom response. This will be administered by a dietitian already specially trained in delivering the low FODMAP dietary intervention, via four sessions (three face-to-face, and one via the telephone).			
	2. Low-dose amitriptyline. This will be commenced at a dose of 10mg (one tablet) at night, and dose titration will occur, to a maximum of 30mg once			

	daily (OD) at night (three tablets), de to treatment.	epending on side effects and response		
	3. Ondansetron. This will be commenced at a dose of 4mg OD, and dose titration will occur, to a minimum of 4mg every week if constipation occurs, or a maximum of 24mg per day, depending on side effects and response to treatment.			
	4. Loperamide. Participants will be given the option to commence at a dose of 4mg per day, with dose titration occurring up to a maximum of 16mg per day, or to use this on an as required basis, depending on side effects and response to treatment.			
	5. Control intervention - standard first-line dietary advice, in the form of the British Dietetic Association (BDA) food fact sheet for people with irritable bowel syndrome (IBS), which is endorsed by the National Institute for Health and Clinical Excellence.			
	Participants in all active intervention arms will also receive the BDA food fact sheet for people with IBS. They will be advised not to alter their diet in any other way, unless they are in the low FODMAP diet arm of the trial. Once participants are recruited, they will be asked not to adjust or change any other over-the counter or prescribed medications for their UC.			
	Please refer to section 8 for full details of the interventions.			
Randomisation	Randomisation will be carried out by the Clinical Trials Research Unit (CTRU). Randomisation will be via minimisation at the level of the individual, stratified according to centre, degree of discomfort from diarrhoea, extent of UC, and Hospital Anxiety and Depression Scale (HADS)-Depression score.			
	During the phase 2 period participants will be randomised in the ratio 1:1:1:2, with the larger group receiving the control intervention. During the phase 3 period this will be reversed to 2:1, or 2:2:1, depending on the number of active interventions taken forward.			
	Objectives	Outcome Measures		
Primary: phase 2	What is the short-term effectiveness of low FODMAP diet, low-dose amitriptyline, ondansetron, and	GSRS-IBS questionnaire at 8 weeks post-randomisation: improvement defined as those reporting minor		
	loperamide, each compared with a control of standard first-line dietary advice, in terms of improvement in diarrhoea symptoms?	discomfort from diarrhoea or less (scoring ≤2 on the diarrhoea subscale).		

Primary: phase 3	What is the effectiveness of a maximum of two interventions continued from phase 2 (having shown evidence of short-term effectiveness) in terms of improved disease-specific quality of life?	Inflammatory Bowel Disease Questionnaire overall score at 6 months post-randomisation (measuring bowel symptoms		
Secondary: phase 2 and 3.	a. What is the effect of the active treatments, compared with a control of standard first-line dietary advice, in terms of improvement in discomfort from loose stools, diarrhoea, urgency, and abdominal pain?	All secondary outcomes are measured at both 8 weeks and 6 months: a. GSRS-IBS;		
	 b. Markers of disease activity, including escalation of medical therapy, need for surgery, FC, and CRP? c. Improvement in the participants overall mood? 	 b. Blood for CRP, stool for FC at 6 months only, reviewing case notes for escalation of medical therapy for UC; 		
Other outcomes of interest	What is the safety and tolerability of the active treatments?	 c. HADS. Safety assessed through collection of adverse events (AEs) and serious adverse events (SAEs) including AEs of special interest. Tolerability assessed via drop-out rates due to AEs, rates of constipation collected via the GSRS-IBS, and confirmed flares of disease activity at 8 weeks and 6 months. Drop-out rates in the low FODMAP arm for any reason pertaining to the intervention will also be taken into account when assessing tolerability. 		

What is the adherence to each of the active treatments, compared with a control of standard first-line dietary advice?	Adherence to IMP (amitriptyline, ondansetron, loperamide) at 6 months is measured by self-report on the participant questionnaires (see section 13.3.10).
	 Adherence to low FODMAP diet at 8 weeks and 6 months is determined using a 4-point Likert scale: Adherence is defined as a Likert response of 1, 2, or 3 (4 is defined as not adherent).

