3.3 Secondary Objectives

Our secondary objectives are to answer the following questions at both 8 weeks and 6 months:

- 1. What is the effect of the active treatments, compared with a control of standard firstline dietary advice, in terms of:
 - a. Improvement in discomfort from (i) loose stools, (ii) diarrhoea, (iii) urgency, and (iv) abdominal pain, each assessed via the GSRS-IBS [26]?
 - b. Markers of disease activity, including escalation of medical therapy, need for surgery, faecal calprotectin (FC), and C-reactive protein (CRP)?
 - c. Mood, via the hospital anxiety and depression scale (HADS) [28]?
- 2. What is the tolerability and safety of the active treatments, compared with a control of standard first-line dietary advice?
- 3. What is the adherence to each of the active treatments, compared with a control of standard first-line dietary advice?

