4.4 Internal Pilot

An internal pilot, across a minimum of 10 centres, will assess recruitment, treatment dropouts, adherence to a low FODMAP diet, and follow-up rates. Rates will be monitored monthly by the Trial Management Group (TMG), to identify, proactively, centres below target requiring additional support to improve progress.

Progression criteria are:

Recruitment rates will be assessed after 6 months of recruitment. Rates will be calculated from recruitment in each of the 6 sites in months 4 to 6 to allow time for recruitment to stabilise:

□ Green/Continue: At least 80% of target recruitment (>80% of 1.4 pts/site/month)

□ Amber/Review: 50%–80% of target recruitment rate

□ Red/Stop: Less than 50% of target recruitment rate

Treatment drop-out will be assessed 6 months later, i.e. after 12 months of recruitment: Green/Continue: No more than 20% of patients withdraw from any one of the active treatments

□ Amber/Review: No more than 40% of patients withdraw from any one of the active treatments

□ Red/Stop: More than 40% of patients withdraw from one or more the active treatments

Adherence to a low FODMAP diet will be assessed after 12 months of recruitment:

- □ Green/Continue: At least 80% of patients adhere to diet
- □ Amber/Review: 60-80% of patients adhere to diet

□ Red/Stop: Less than 60% of patients adhere to diet

Follow-up rates will be assessed after 12 months of recruitment

□ Green / continue: At least 80% follow-up

Amber / review: 60-80% follow-up

□ Red/stop: Less than 60% follow-up

If any criteria are amber, we will review trial processes comprehensively and develop a rescue plan, approved by the Trial Steering Committee (TSC), which will be submitted to the HTA. If the treatment drop-out or adherence criteria are red, this will result in the relevant treatment arm(s) being dropped from the trial. If the recruitment or follow-up criteria are red, the TSC will consider not progressing the pilot to the definitive trial.

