8.1.4 Delivery of intervention

Dietitian Appointment 1 (within 1 week of randomisation)

In the first session with the dietitian, education will be given to each participant covering the mechanistic actions of FODMAPs in the gut, high FODMAP-containing food sources to avoid, and medium and low levels that can be included per meal session, including suitable food products to include in their diet. Two written comprehensive educational booklets (copyright Guy's and St Thomas' NHS Foundation Trust and King's College London) will be used which will be given to each participant to take home. More details on these resources can be found in the TiDIER checklist, Appendix 1. Dietary counselling will involve practical information on meal and snack ideas in line with healthy eating principles, meal planning, recipe modification, reading food labels, eating out tailored to the participants will be encouraged to review the information provided during the session at home and plan grocery shopping, meals, and snacks to incorporate the low FODMAP restriction into their daily activities.

Dietitian Appointment 2

After 8 weeks on the low FODMAP diet (**the restriction stage**), each participant will attend a second face-to-face 30-minute session held at the site's usual outpatient dietetic clinic room setting.

In this session the dietitian will decide whether the patient has positively responded to the intervention by assessing adherence to the low FODMAP diet and whether overall gastrointestinal symptoms have improved. Those who do not respond or adhere to the low FODMAP diet will return to their usual diet. Those who respond to the low FODMAP dietary intervention will progress to the next stage of the diet, **the reintroduction stage**, and will receive a third booklet outlining the process of reintroduction and personalisation. If more convenient, the third booklet may be supplied to the participant at Dietitian Appointment 1 with the first two comprehensive booklets and participants advised not to use the third booklet until their 8-week Dietitian Appointment 2. The dietitian will advise the participant on when to reintroduce FODMAP subgroups, the quantity of food to reintroduce, and the ordering of reintroduction. This is done to help increase dietary variety whilst keeping diarrheal symptoms under control.

Telephone Review

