8.7 Discontinuation of Study Treatment

In line with usual clinical care, cessation or alteration of regimens at any time will be at the discretion of attending clinicians, or the participants themselves. All participants who discontinue from treatment, or who are prescribed alternative treatment, will still attend for follow-up assessments and complete questionnaires, unless they withdraw from the trial (see section 10). Data pertaining to safety will continue to be collected for regulatory reporting purposes and will be included in any safety analysis. The reason for discontinuing study medication will be recorded. Reasons for study treatment discontinuation include:

- Patient decision;
- Severe non-compliance to this protocol as judged by the investigator;
- Safety, including allergic reaction to IMP;
- If the investigator considers that a patient's health will be compromised due to AEs or concomitant illnesses that develop after entering the study;
- Receipt of a restricted concomitant medication after entering the study;
- Pregnancy;
- Overdose;
- Suicidal ideation;
- Flare of disease activity.

Once study medication is permanently discontinued it cannot be restarted as part of the study. Patients should return all unused IMP on cessation of trial treatment. If a participant withdraws from treatment, a Treatment Discontinuation CRF should be completed by the site.

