13.3.5 Descriptive Statistics

Descriptive statistics will be presented for demographics and baseline data, endpoints, and safety data. Continuous variables will be summarised by mean, SD, median, minimum, and maximum, as well as interquartile range, if appropriate. Categorical variables will be summarised by frequencies and percentages. A CONSORT diagram will display the flow of participants through the trial. Baseline characteristics of those lost to follow-up will be compared with those not lost to follow-up to assess for bias, and to inform the methods for handling missing data in inferential analyses.

13.3.6 Phase 2 Analysis and Progression to Phase 3

At the end of the phase 2 period, the diarrhoea responder rates at 8 weeks will be compared between the control group and each of the intervention arms individually, in logistic regression models adjusted for the stratification factors. Results will be expressed as odds ratios, together with 80% confidence intervals and p-values. Intervention arms will only be carried forward to phase 3 if the p-value in comparison with the control group is <0.2. This will correspond to an odds ratio >2, or to an absolute difference in response rate of 17%, when compared with the control group, if the response rate in the control group is 33%. If more than two intervention arms achieve this difference, the observed response rates, as well as safety, will be taken into account to decide which treatment arms should progress.

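### Drop-out as a tolerability measure is counted more widely in the low FODMAP arm than in any other arm, with no reason given, so that item is not like for like

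*Protocol*

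**What the plan says.** The Protocol's Trial Summary, under Other outcomes of interest, sets the general rule: "Tolerability assessed via drop-out rates due to AEs, rates of constipation collected via the GSRS-IBS, and confirmed flares of disease activity". The rule covers both follow-up time points and is not limited to particular arms. The next sentence adds an item for one arm: "Drop-out rates in the low FODMAP arm for any reason pertaining to the intervention will also be taken into account when assessing tolerability". Nothing equivalent is stated for amitriptyline, ondansetron, loperamide or control.

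Section 3.3 makes tolerability a comparative question: "What is the tolerability and safety of the active treatments, compared with a control of standard first-line dietary advice".

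Three other places bear on how drop-out is understood:

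- Section 4.4 sets the internal pilot criterion on treatment drop-out. Its green level is "No more than 20% of patients withdraw from any one of the active treatments". It does not restrict by reason and applies alike to all active arms.
- Section 8.7 says of the drug arms "The reason for discontinuing study medication will be recorded", and asks for a Treatment Discontinuation CRF when a participant withdraws from treatment.
- Section 8.1.4 says of the week-8 dietitian visit: "Those who do not respond or adhere to the low FODMAP diet will return to their usual diet".

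**The concern.** An outcome meant for comparison between arms should be ascertained in the same way in each arm. Here one component has a wider numerator in a single arm. A participant who stops a study drug because it does not help, or because titrating it is a nuisance, is not a tolerability drop-out unless an AE was the cause. A participant who gives up the diet for the same kind of reason is. The control is also dietary advice, yet the wider item is not applied to it.

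What is at stake is the reading of secondary objective 2. A table that shows diet drop-out for any intervention-related reason beside AE-only drop-out elsewhere would show a gap produced partly by the definition. Readers who set the diet beside the drugs would meet the same problem.

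**Working it through.** The Protocol states no drop-out rate, so it has no figure of its own to reproduce. The check is to write out the two numerators and see what they do under assumed rates.

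**Inputs**

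- Phase 2 arm size: 66 per intervention arm and 132 in control (Protocol Section 13.1.1).
- a = proportion stopping because of an AE. Assumed, 2% to 10%.
- b = proportion stopping for another intervention-related reason. Assumed, 5% to 15%.

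**What is counted under the Trial Summary**

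- Drug arm: n × a
- Control: n × a
- Low FODMAP arm: n × (a + b)

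With the same a and b in every arm, the excess in the diet arm is n × b. This is never negative, so at equal true drop-out the item can only add to the diet arm.

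**Example with a = 5% and b = 10% in every arm**

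- Drug arm: 66 × 0.05 = 3.3
- Diet arm: 66 × (0.05 + 0.10) = 9.9
- Excess from the definition alone: 66 × 0.10 = 6.6
- Against control, as rates: 15% for diet and 5% for control, where a common definition gives 15% in both or 5% in both

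**Range of the assumed rates (counts of 66)**

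| a | b | Drug arm | Diet arm | Excess |
|---|---|---|---|---|
| 2% | 5% | 1.3 | 4.6 | 3.3 |
| 5% | 5% | 3.3 | 6.6 | 3.3 |
| 5% | 10% | 3.3 | 9.9 | 6.6 |
| 5% | 15% | 3.3 | 13.2 | 9.9 |
| 10% | 15% | 6.6 | 16.5 | 9.9 |

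The excess runs from 66 × 0.05 = 3.3 to 66 × 0.15 = 9.9 participants and does not depend on a. With one definition in all arms it is 0.

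**Does the definition settle the ranking?** No. Suppose a drug arm has 10% AE drop-out and the diet has 5% drop-out in total. The counts are 66 × 0.10 = 6.6 and 66 × 0.05 = 3.3, and the diet still looks better.

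**The week-8 boundary.** Section 8.1.4 has the dietitian return non-responders and non-adherent participants to their usual diet. Non-response could be read as an intervention-related reason. However, the Protocol nowhere calls these participants drop-outs, and it keeps them in follow-up with a research nurse visit at 24 weeks. The Trial Summary does not say which side of the line they fall on.

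**The case against.** The wider diet item is a defensible design judgement. The AEs listed in Section 11.2 are largely drug-type effects such as dry mouth, drowsiness and dizziness. A restrictive diet may be abandoned for reasons that are not AEs, so AE-only drop-out could flatter it. This has force, but the Protocol does not give it as its reason. It supports keeping the wider rate, not confining it to one arm, because participants on drugs can also stop for non-AE reasons.

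The diet sentence adds an item and does not set a single composite rate. The AE drop-out rate applies to every arm, so a like-for-like comparison on that rate remains available. Tabulation is ordinary SAP content, and the SAP is not at hand. This stands, and it limits the finding to the extra item.

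The stakes are also low. Tolerability is an other outcome of interest, constipation and flares count in all arms, and no primary result depends on the diet-only item.

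A reader might draw three stronger conclusions, which the documents do not support:

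- *The diet must look less tolerable by definition.* The ranking depends on the data, as the last example shows, and drop-out is only one of the components.
- *About half the diet arm could be labelled drop-outs at week 8.* This would borrow the 50% response assumed in Section 13.1.1, which is a planning value for a GSRS-IBS diarrhoea score. The week-8 decision rests on the dietitian's view of adherence and of gastrointestinal symptoms overall, for which the Protocol assumes no rate.
- *The asymmetry biases which arms reach phase 3.* If more than two arms qualify, Section 13.3.6 says "the observed response rates, as well as safety, will be taken into account to decide which treatment arms should progress". Tolerability is not named there, and the Trial Summary describes safety separately from it. The pilot drop-out rule, which can remove an arm, is the same for every active treatment.

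**Conclusion.** The concern holds as a minor point. The Trial Summary fixes a drop-out item for tolerability that applies to the low FODMAP arm only, without a reason, although Section 3.3 makes tolerability a comparison with control. At equal true drop-out, the diet arm is charged with extra tolerability drop-outs equal to its other intervention-related drop-out: 6.6 of 66 in the main example, and 3.3 to 9.9 over the range tried. These sizes rest wholly on assumed rates and on equal true rates in every arm. The direction of the effect needs only the equal-rates assumption. The finding concerns this one item. It does not show that tolerability as a whole is tilted against the diet, or that progression to phase 3 is affected.

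**What to change.** Replace the diet-only sentence with two rates, defined identically and reported for every arm:

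- (a) discontinuation of the allocated intervention due to an AE;
- (b) discontinuation for any intervention-related reason, including AEs, burden or inconvenience, and perceived lack of effect.

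Take both from the Treatment Discontinuation CRF. Section 8.7 records the reason for stopping study medication, so confirm that the form also captures reasons in the low FODMAP and control arms, and state what discontinuation means for participants given dietary advice only. Tabulate return to usual diet at Dietitian Appointment 2 separately, and state that it is not drop-out.

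If the diet-only item is kept, give the reason for it and make no comparison between arms on that measure.

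The cost is a wording change in the Trial Summary, a matching line in the SAP, one more row in the tolerability table and a check of the CRF for the non-drug arms. Sample size, primary analyses and visits are unaffected.

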8.1.5 Monitoring Participant Adherence

Adherence at 8 weeks and 6 months will be determined using a 4-point- Likert scale [33] (scored 1 – continued a strict low FODMAP diet; 2 – reintroduced high FODMAP foods to tolerance; 3 – continued a low FODMAP diet 50% of the time; 4 – returned to habitual diet). Analysis of FODMAP content will be via the Comprehensive Nutrition Assessment Questionnaire (CNAQ) [34] in all participants, in order to verify that the FODMAP content is less in the low FODMAP diet arm at 8 weeks, compared with the other four trial arms. The CNAQ is a semi-quantitative food frequency questionnaire validated to assess FODMAP and nutrient intake, and is determined using an online automated entry system (http://www.cnaq.com.au)

Participants who are classed as non-adherent after the 8-week restriction phase will be classed as non-responders and will be instructed to return to their usual diet. This will include any participants who do not respond with an answer of 1, 2, or 3 to the adherence question.

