13.3.3 Analysis Populations

Analyses will be on the ITT population, which will include all randomised participants, analysed according to the study arm to which they were randomised, irrespective of adherence to treatment. A per protocol analysis of the primary outcome will also be conducted, based on pre-defined criteria associated with intervention adherence.

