13.3.10 Adherence

Adherence at 8 weeks and 6 months in the IMP arms is measured by a 4-point-Likert scale.

Adherence will also be assessed via a summary question at 8 weeks and 6 months. For the Amitriptyline arm, the question will be as follows:

""Since you were last asked, which of the options best describes how often you have taken at least one tablet of the trial medication daily?"

- A. Every day or nearly every day
- B. Half of the days or more than half of the days
- C. Less than half of the days
- D. None or nearly none of the days"

For the Ondansetron and Loperamide arms, the summary question at 8 weeks and 6 months will be as follows:

""Since you were last asked, which of the options best describes how often you have taken at least one tablet of the trial medication weekly?"

- A. Every week or nearly every week
- B. Half of the weeks or more than half of the weeks
- C. Less than half of the weeks
- D. None or nearly none of the weeks"

Descriptive statistics, by arm, will be summarised to show the number of adherent patients at each time point, for both of the methods described above.

For those randomised to a low FODMAP diet, adherence at 8 weeks and 6 months will be determined using a 4-point-Likert scale [33]. The question and responses will be as follows:

"Which of the following best describes your adherence to the Low FODMAP diet?"

- A. Continued strict low-FODMAP diet
- B. Reintroduced high-FODMAP foods to tolerance
- C. Continued low-FODMAP diet 50% of the time
- D. Returned to habitual diet

Descriptive statistics will be summarised and presented alongside results of the adherence summary question in the IMP arms, as described above.

FODMAP content will be assessed at 8 weeks and 6 months via the CNAQ [34] in all participants, in order to verify that the FODMAP content is less in the low FODMAP diet arm at follow-up, compared with the other four trial arms. Descriptive statistics only will be presented for the FODMAP content, which will be displayed by arm.

The CNAQ is a semi-quantitative food frequency questionnaire validated to assess FODMAP and nutrient intake, and is determined using an online automated entry system.

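### The 6-month low FODMAP adherence rule counts participants as not adherent for following the protocol's own instruction to return to their usual diet

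*Protocol*

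**What the plan says.** **The adherence rule.** For the low FODMAP arm, the Trial Summary (other outcomes of interest) states: "Adherence is defined as a Likert response of 1, 2, or 3 (4 is defined as not adherent"). Section 8.1.5 applies one scale at both visits: "Adherence at 8 weeks and 6 months will be determined using a 4-point- Likert scale". It labels the lowest category "4 – returned to habitual diet". Section 13.3.10 repeats the scale with letters A to D. Adherence is a secondary objective at both time points (section 3.3, item 3).

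**The pathway after week 8.** At Dietitian Appointment 2 the dietitian judges adherence and whether overall gastrointestinal symptoms have improved. Section 8.1.4 then says: "Those who do not respond or adhere to the low FODMAP diet will return to their usual diet". Section 8.1.5 adds, of the diet they go back to: "Participants who are classed as non-adherent after the 8-week restriction phase will be classed as non-responders and will be instructed to return to their usual" one. Item 9 of the TIDieR table (Appendix 4) gives the same instruction. Only responders go on to reintroduction.

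**Where adherence is used.** Section 13.3.10 plans descriptive summaries. Section 13.3.3 says: "A per protocol analysis of the primary outcome will also be conducted, based on pre-defined criteria associated with intervention adherence". Section 13.3.7 gives that analysis the role of testing robustness. Section 4.4 sets pilot bands for diet adherence (green at 80% or more, red below 60%) and says: "If the treatment drop-out or adherence criteria are red, this will result in the relevant treatment arm(s) being dropped from the trial". Sections 3.4, 4.4 and 13.3.2 say the criterion is examined after 12 months of recruitment. They do not say whether the week-8 or the 6-month answer counts.

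**The concern.** The 6-month rule and the week-8 instruction contradict each other. Someone who restricted FODMAPs strictly for 8 weeks without benefit has done all that the protocol asked. They are told to resume their usual diet, and the only truthful answer at 6 months is then category 4. The protocol calls that not adherent.

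The certain consequence is that the 6-month adherence result, a stated objective, does not measure adherence to the intervention as designed. It partly measures how many people responded at week 8.

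Two further consequences depend on choices that the protocol leaves open:

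- The per-protocol criteria rest on adherence, and the phase 3 endpoint is at 6 months. If the 6-month score were used, the diet arm would lose participants because they did not respond, while control would keep all of its own.
- The pilot criterion can remove the arm from the trial. If the 6-month score were used, an arm in which everyone followed the protocol could be classed red.

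**Working it through.** The protocol gives no figure to reproduce on this point. The check sets the passages side by side and then asks how far the 6-month score can move.

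**Step 1. Pathways through the diet arm** (sections 8.1.4, 8.1.5 and Appendix 4)

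| Restriction to week 8 | Symptoms at week 8 | Protocol instruction | Behaviour afterwards | Truthful 6-month score | Counted as |
|---|---|---|---|---|---|
| Adherent | Improved | Reintroduce | Follows it | 1 to 3 | Adherent |
| Adherent | Improved | Reintroduce | Abandons the diet | 4 | Not adherent |
| Adherent | Not improved | Usual diet | Follows it | 4 | Not adherent |
| Not adherent | Either | Usual diet | Follows it | 4 | Not adherent |

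The third row is the contradiction. Category 4 also merges three different groups, so the 6-month score alone cannot separate them.

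**Step 2. Understatement of 6-month adherence**

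Let u be the share of the arm in the third row's position (adherent to week 8, not improved, sent back), and g the share of those who nevertheless answer 1 to 3. Compared with a count of people who followed the pathway:

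understatement = u × (1 − g)

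If all comply (g = 0), it equals u. The protocol gives neither value. The 50% and 33% in section 13.1.1 are design rates for a GSRS-IBS diarrhoea score of 2 or less. The dietitian's decision concerns overall gastrointestinal symptoms, so those rates cannot stand in for it.

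**Step 3. Break-even against the pilot bands, if the 6-month score were used**

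Take the most favourable arm: everyone adherent to week 8, and every responder still scoring 1 to 3 at 6 months. Then u is the whole share sent back, and

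6-month adherence = 1 − u × (1 − g)

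- g = 0: adherence is below 80% once u exceeds 20%, and below 60% once u exceeds 40%.
- g = 0.25 (assumed): adherence is below 60% once u exceeds 0.40 / 0.75 = 53.3%. At u = 50% it is 1 − 0.50 × 0.75 = 62.5%, which is amber.

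Scored at week 8, the same arm is at 100%, which is green. The result therefore depends on which visit is read, and section 4.4 does not say.

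**Step 4. Direction of the per-protocol effect, if the 6-month score were used**

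Let p be the share of the diet arm removed, K the mean 6-month IBD-Q of those kept and R that of those removed. The whole-arm mean is (1 − p)K + pR, so the shift from removal is

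K − [(1 − p)K + pR] = p × (K − R)

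This favours the diet whenever those who improved at week 8 have better quality of life at 6 months than those who did not (K > R). That is plausible but assumed. Control has no matching removal. Neither p nor K − R is in the protocol. The 16 to 32 points in section 13.1 are bounds for a meaningful within-patient change, not a gap between responders and non-responders. If the week-8 answer, given before anyone is sent back, defines the set, this mechanism does not arise.

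**The case against.** The strongest reply is that little hangs on the label. The primary analysis is intention-to-treat, irrespective of adherence. Section 13.3.10 plans only descriptive use of the scale. Describing what participants were actually eating at 6 months is a legitimate aim, and category 4 does that correctly. This stands as far as it goes, but the protocol does more than describe diet: it names category 4 not adherent at a visit where it has itself sent people into that category.

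A reader might infer that the per-protocol set will consist mainly of responders and will inflate the diet effect by some number of IBD-Q points. The document does not support that. Section 13.3.3 ties the set to adherence in general and names neither the 6-month score nor a cut-off. The criteria may properly sit in a statistical analysis plan that is not shown, and any numerical bias would rest on invented inputs. The analysis is also only a sensitivity analysis, and at phase 3 it concerns the diet only if that arm is carried forward.

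On the pilot, section 3.4 attaches 6 months to follow-up and not to diet adherence, and section 8.1.5 attaches consequences only to non-adherence after the 8-week restriction. Week 8 is therefore the likelier intention. It is still unstated for a rule that removes an arm.

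Two other extensions fail:

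- **Pilot drop-out criterion.** A reader might add that directed return to usual diet would count as treatment drop-out. Section 4.4 counts withdrawals from treatment, and section 8.7 does not list a directed return among its reasons for discontinuation.
- **Loperamide.** A reader might say that as-required users are scored as poor adherers by the question asking "which of the options best describes how often you have taken at least one tablet of the trial medication weekly". Section 13.3.10 sets no adherent/non-adherent cut-off for the drug arms, so nothing scores them that way.

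**Conclusion.** The contradiction is in the current text and holds without assumptions about rates: the 6-month rule misclassifies people who follow the week-8 instruction. If the rule is applied as written, 6-month adherence in the low FODMAP arm is understated by the share of adherent non-responders who comply, and it varies with week-8 response. That share cannot be obtained from the protocol.

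The per-protocol and pilot consequences are risks and not established faults. The per-protocol effect would favour the diet if the 6-month score defined the set and if week-8 improvement goes with better 6-month IBD-Q. The red pilot classification needs the 6-month reading and, under full compliance and otherwise perfect adherence, more than 40% of the arm sent back. The intention-to-treat primary analysis does not change. The point still merits correction because one of the open choices feeds an arm-dropping rule.

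**What to change.** Three changes of wording reconcile the passages. None alters who is sent back to usual diet, which is a clinical rule and outside this point.

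1. **Trial Summary, sections 8.1.5 and 13.3.10.** Classify 6-month adherence against the protocol pathway. A directed return to usual diet after an adherent 8-week restriction either counts as following the intervention or is reported as its own category, separate from week-8 non-adherers and from responders who later abandoned the diet.
2. **Section 4.4.** State that the pilot adherence criterion uses the week-8 assessment.
3. **Section 13.3.3, or the analysis plan it relies on.** Base per-protocol status in this arm on adherence to the week-8 restriction and not on the 6-month score. Adherence at week 8 may still be related to how people feel, but the built-in link with response is removed.

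The cost is close to nothing. The week-8 score is already collected, and the dietitian's week-8 decision already determines who receives the week-16 call. The trial team need only confirm that this decision is recorded on the case report form.
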